### **B.6.9. UNSCHEDULED VISITS**

Unscheduled visits may occur at any time during the study for the assessment of possible study-related adverse events, changes in pain medication, and programming adjustments. Each unscheduled visit will be documented and recorded in the corresponding case report form (CRF).

### **B.6.10. TELEPHONE CALLS**

Subjects will be contacted by the study coordinator, via a telephone call, before each study visit. The study coordinator will check on the well-being of the subject, remind the subject of the upcoming scheduled visit, remind the subject not to change pain medication usage prior to the scheduled visit, and remind the subject to contact the Investigator/study staff should he/she have any concerns or questions. The telephone calls should be made two to three weeks *before* the scheduled visit.

### **B.6.11. 1 MONTH AFTER DEVICE ACTIVATION ( $\pm$ 15 DAYS)**

Subjects will visit the study site where they will be assessed for pain intensity. Programming adjustments may be made, as needed. Anterior-posterior (AP) and lateral X-ray imaging may be done if significant lead migration is suspected. Subjects will be assessed for study-related adverse events and medication usage.

### **B.6.12. 3 MONTHS AFTER DEVICE ACTIVATION ( $\pm$ 21 DAYS)**

Subjects will visit the study site where they will be assessed for pain, other pain (if applicable), extent of disability, Patient Global Impression of Change, and subject satisfaction. Paresthesia generated by the stimulator will be assessed. Programming adjustments may be made, as needed. Anterior-posterior (AP) and lateral X-ray imaging will be done. Subjects will also be assessed for possible study-related adverse events and medication usage. If there are no ongoing study-related adverse events, the subject will complete the study at this visit. In situations where there is an ongoing study-related adverse event, subjects will be followed until resolution of that adverse event or determination that the subject's condition is stable, at which point the Study Completion CRF should be completed.

### **B.6.13. 6 MONTHS AFTER DEVICE ACTIVATION ( $\pm$ 31 DAYS)**

. The 6 Months visit will consist of the same assessments as the 3-month visit except the anterior-posterior (AP) and lateral X-ray imaging is optional. Subjects will visit the study site where they will be assessed for pain, extent of disability, quality of life, Patient Global

Impression of Change, and subject satisfaction. Paresthesia generated by the stimulator will be assessed. Programming adjustments may be made, as needed. Subjects will also be assessed for possible adverse events and medication usage. In situations where there is an ongoing study related adverse event, subjects will be followed until resolution of that adverse event or determination that the subject's condition is stable.

However, all subjects who remain implanted at the time of Study Completion will be offered to return for an additional visit 12-months after device activation.

Following the last scheduled study visit, subjects will be followed by their pain physician at regular intervals, as dictated by standard of care at each site, in order to facilitate pain management, stimulation adjustments, possible revisions and/or replacements of neurostimulation components. Any additional non-study related monitoring of the subject will be the responsibility of the subject's personal physician, as dictated by reasonable medical care.

#### **B.6.14. 12 MONTHS AFTER DEVICE ACTIVATION ( $\pm$ 31 DAYS)**

Subjects will be offered an optional visit at 12 months after device activation. This visit will consist of the same assessments as the 6-month visit. Subjects will visit the study site where they will be assessed for pain, extent of disability, quality of life, Patient Global Impression of Change, and subject satisfaction. Paresthesia generated by the stimulator will be assessed. Programming adjustments may be made, as needed. Subjects will also be assessed for possible adverse events and medication usage. In situations where there is an ongoing study related adverse event, subjects will be followed until resolution of that adverse event or determination that the subject's condition is stable.

Following the last scheduled study visit, subjects will be followed by the Investigator at regular intervals, as dictated by standard of care at each site, in order to facilitate pain management, stimulation adjustments, possible revisions and/or replacements of neurostimulation components. Any additional non-study related monitoring of the subject will be the responsibility of the subject's personal physician, as dictated by reasonable medical care.

#### **B.6.15 OTHER ASSESSMENTS AND INFORMATION**

At any time during the study, if lead migration is suspected, the subject may have additional AP and lateral X-rays taken to confirm the new lead position in order to aid the Investigator in determining a course of action.

Paresthesia testing may also be performed to assess lead location and therapy coverage of pain areas. Programming adjustments may be made based on patient feedback following assessment.

Additional information on Medication Usage:

- The Investigator will instruct all subjects to take the Baseline doses of pain medication until the 3-Month Visit. However, after Device Activation Visit, the Investigator may reduce the dose of pain medication if the subject is benefitting greatly from DTM SCS therapy and not benefitting from Baseline dose pain medication.
  - Subjects should not fluctuate medication usage nor dosages even if the dose is at or below Baseline doses. The Investigator/Study staff will instruct all subjects to maintain stable dosing of medication for at least two weeks prior to scheduled follow-up visits.
- Following trial and permanent implants, the clinical site's standard practice for prophylactic pre-surgery antibiotics and post-surgery pain medications will be followed. Investigators/Study staff will instruct subjects not to change usage of any other concomitant pain medications.

Remote data collection from the subjects is allowed. This should be evaluated on a case by case basis, pending Investigator's approval based on safety and clinical condition. Subjects who are not demonstrating study compliance, e.g. not returning phone calls, not charging device or turning the device off should not be mailed study questionnaires until they demonstrate compliance with the study. The site should continue to contact the subject and ensure compliance before mailing the questionnaires. The communications will be documented in the source worksheets. Remote visits would apply to any visit that could be conducted remotely without the subject being present, including remote programming, if available. Procedural visits (trial and IPG) and any unscheduled visits required for study-related adverse events would continue to be performed in office where possible.

- Visit windows remain in place and should be maintained as much as possible. Subjects should be contacted via phone to collect AEs, medications and concurrent procedures. All questionnaires required at a visit should be obtained via phone, email or via mail based on site and/or subject preference.
- If by phone: site staff will read each question to the subject and record their answers. The site staff should initial and date the bottom of each form and indicate that it was completed via phone.
- If by email: the site staff should send the study questionnaires. Subjects can either print and manually complete or complete the forms electronically.
- If manually completed (printed): the subject will be instructed to initial and date each page and scan and email or mail the responses back to the site.
- If the forms are completed electronically: the subject will be instructed to complete the questionnaires and return the responses to the site as soon as possible, ideally, within 3 business days.

- If the questionnaires are sent in hard copy by mail: the subject should be instructed to complete the questionnaires and initial and date each page after completion and return to site as soon as possible. Ideally, within 3 business days of receipt.
- Source documentation should clearly describe the process utilized for each subject at each visit when these alternative methods are utilized.

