### **B.6.17. EARLY SUBJECT WITHDRAWAL**

Although efforts will be made by Investigators and study staff to encourage eligible subjects to remain enrolled in the study, subjects may withdraw early from the study for a number of reasons, including but not limited to:

- Failure of SCS Trial Phase
- Subject request
- Investigator request
- Subject lost to follow-up
- Subject's death
- Adverse events (e.g., intolerable adverse event occurrence that forces subject to stop participation in the study)

If a subject is considering withdrawing from the study due to unsatisfactory effectiveness of DTM SCS programming, the Investigator will attempt to improve therapy during a study visit. When a subject is withdrawn early from the study, a Study Termination CRF will be completed describing the reason for discontinuation. Study staff will contact subjects to remind them about their scheduled visits and make sufficient efforts to locate a subject that is not responding to a contact call. If a subject has withdrawn consent for the study, or is lost to follow-up, the completion of this visit is not required. In situations where study withdrawal is due to a study-related adverse event, subjects will be followed until resolution of the adverse event or determination that the adverse event is not likely to change.

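### At remote visits, mailing of outcome forms depends on the subject charging and using the device, and no route is named for subjects held back

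*Combined protocol and SAP*

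**What the plan says.** Section B.6.15 allows remote data collection case by case, with the Investigator's approval. It then says that subjects "not demonstrating study compliance, e.g. not returning phone calls, not charging device or turning the device off should not be mailed study questionnaires" until they show compliance. It adds: "The site should continue to contact the subject and ensure compliance before mailing the questionnaires". The contacts are to be recorded: "The communications will be documented in the source worksheets".

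The bullets that follow in the same section keep the visit windows, as far as possible, and state: "All questionnaires required at a visit should be obtained via phone, email or via mail based on site and/or subject preference".

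Other sections bear on how far the hold reaches:

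- **B.6.12** makes attendance the default at 3 months: "Subjects will visit the study site where they will be assessed for pain, other pain (if applicable), extent of disability". It also requires AP and lateral X-rays at that visit.
- **C.1 (Study Risk Control Measures)** lets subjects turn stimulation off at any time during the study.
- **B.6.17** asks staff to "make sufficient efforts to locate a subject that is not responding to a contact call".
- **B.7.3** defines a responder by a fall of at least 50% in upper limb VAS from Baseline to 3 months after activation, so the classification needs a 3-month score.

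**The concern.** The hold makes collection of a pain outcome conditional on use of the treatment whose effect on pain is being measured. Poor relief is one plausible reason to switch a stimulator off or stop charging it. If so, the subjects held back would include more non-responders than the rest.

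Two things could then happen. The form may never be obtained. Or it may be obtained only once stimulation has resumed, and so record relief that was absent while the form was withheld. Either would tend to raise the reported responder percentage, and a single-arm study has no comparator in which the distortion would show. The second route can operate inside the visit window, where no deviation would mark it.

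**Working it through.** **Step 1: the rules side by side.**

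- *Trigger:* not charging, or device off (B.6.15). Switching off is something the plan permits (C.1), so permitted behaviour can start the hold.
- *Release:* evidence of compliance, with compliance placed before mailing (B.6.15). No maximum duration is given.
- *Window:* maintained as far as possible (B.6.15); ±21 days at 3 months (Table 1). Nothing says what happens if the window closes during a hold.
- *Other routes:* phone and email are listed, chosen by site or subject preference (B.6.15). The hold bars only mailing. These routes are not barred, but they are not assigned to held subjects either.

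A site could read the section as leaving phone, email or an office visit open, or as postponing the forms until the subject complies. The text does not settle which.

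**Step 2: exposure by visit.** VAS is collected at months 1, 3, 6 and 12 (Table 1). X-ray imaging is required at month 3 and optional at months 1, 6 and 12. A fully remote visit is therefore less likely at 3 months than at the others, although questionnaires could still be separated from the imaging.

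**Step 3: scale.** The plan expects about 45 implanted subjects (B.5.4.1). It gives no responder rate and no number of remote visits or held subjects, so there is no figure of the plan's own to reproduce. Assumptions: 45 implanted; 30 who would be responders if every form were collected without a hold (30/45 = 66.7%); and 1, 2 or 4 affected subjects. None affected is also possible.

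One subject is 1/45 = 2.2 points.

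*Late collection.* If j subjects who would have been non-responders while held record a response after stimulation resumes, the rate is (30 + j)/45:

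- j = 1: 31/45 = 68.9%
- j = 2: 32/45 = 71.1%
- j = 4: 34/45 = 75.6%

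If they still record non-response, the rate stays at 66.7%.

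*Missing.* If k forms are never obtained, r of them from responders, the observed rate is (30 − r)/(45 − k):

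- all non-responders (r = 0), k = 1, 2, 4: 30/44 = 68.2%, 30/43 = 69.8%, 30/41 = 73.2%
- all responders (r = k), k = 1, 2, 4: 29/44 = 65.9%, 28/43 = 65.1%, 26/41 = 63.4%
- k = 3 with r = 2: 28/42 = 66.7%, no bias

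The sign depends on who is held back, which the documents do not tell us.

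**Step 4: what a with-and-without comparison can show.** Take j = 4 late forms and none missing. With those subjects the rate is 34/45 = 75.6%; without them it is 30/41 = 73.2%. Both exceed 66.7%. The comparison shows how far the result leans on the affected forms. It neither corrects the rate nor bounds it.

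**The case against.** The strongest reply is that the hold closes one route, mail, for some subjects in a study whose visits are on site by default. Phone and email remain, windows are kept, staff must keep trying to make contact, and section E.1.2 asks the Investigator to try to obtain incomplete data. Most of this stands and sets the limits of the point. It does not remove the instruction to secure compliance before mailing, and it does not tell a site to use another route for a held subject.

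Four stronger readings are tempting and are not supported:

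- *That the hold leaves no time limit and no alternative at all.* The windows remain, softly worded, and other routes are listed. What is missing is an end to the hold and a link between those routes and held subjects.
- *That the primary endpoint is the main casualty.* The required 3-month X-ray makes that visit the least likely of the four to be fully remote.
- *That the pre-visit call makes matters worse because it does not ask about charging.* Section B.6.10 says "The telephone calls should be made two to three weeks" before the visit, and its content is general: "The study coordinator will check on the well-being of the subject, remind the subject of the upcoming scheduled visit". But if the site does not learn that the device is off, the hold is not triggered.
- *That a delayed VAS should be counted as non-response.* A score taken inside the window and showing at least a 50% fall is a response under B.7.3. Reclassifying it would contradict the plan's own endpoint.

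The study is also descriptive, with no hypothesis (B.9.2), and its precision is modest: the exact 95% interval for 32/45 (71.1%) is 55.7% to 83.6%. One or two affected subjects are small against that. But the interval describes random error, and a one-directional collection rule is not covered by it.

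**Conclusion.** The point holds in a limited form. Where mailed remote collection is used, B.6.15 conditions collection of pain outcomes on charging and device-on status, sets no end to the hold and assigns no other route to held subjects. It also sits awkwardly with the permission in C.1 to switch stimulation off. The exposure is greater at months 1, 6 and 12 than at the 3-month primary endpoint.

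The size is unknown. Each affected subject is worth 2.2 points if 45 are implanted. An upward shift rests on the assumption that device-off subjects tend to have poor relief, which is plausible but not shown. A reader might infer that the reported responder rate is biased in favour of the device; the documents support only that the rule could have this effect.

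Loss of subjects through the completer population (B.7.1) and the absence of a missing-data rule (B.9.2) apply to all missing scores. They should be judged as a separate matter and not counted again here.

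**What to change.** **Wording.** In B.6.15, delete non-charging and device-off status from the grounds for withholding forms, and delete the requirement that compliance precede mailing. Keep continued contact and its documentation. Reconcile the paragraph with the list of remote routes and with C.1 by stating, for example: *Required questionnaires are collected within the visit window, by any permitted route, from every implanted subject still in the study, whatever the charging or on/off status. Device status and completion date are recorded.*

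**Visits already done.** Count from the source worksheets the forms that were withheld or delayed, by visit, and report the number.

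**Analysis.** Keep the B.7.3 responder definition for any VAS taken in the window. As a descriptive check only, show the 3-month responder rate with and without subjects whose form was withheld or delayed. Treatment of missing VAS belongs with any change to B.7.1 and B.9.2.

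**Cost.** A short formal amendment with sponsor, IRB and Investigator approval (E.6), one device-status field and a few more forms. Phone, printed and mailed forms already carry a date under B.6.15, so the completion date is new mainly for forms completed electronically. The retrospective count is only as good as the worksheets. The reported rate may come out slightly lower. The change concerns data collection only and leaves device management as it is.

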### **B.6.16. DEVICE EXPLANT**

At any time during the study, a subject may elect to withdraw from the study and have the SCS device system explanted. Additionally, an Investigator may elect to explant a device due to an adverse event.

The Investigator must follow the appropriate guidelines set forth by the manufacturer of the device for returning the explanted device and/or lead(s) as well as the accessories (charger, patient remote control).

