## **B.7. STUDY ENDPOINTS**

### **B.7.1. DEFINITION OF ANALYSIS POPULATIONS**

All subjects who receive a permanent SCS system implant and complete the study without any major protocol deviations (that would render their data unevaluable).

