### **B.7.3. PRIMARY ENDPOINT**

Pain rating on the 10 cm Visual Analog Scale (VAS) is considered the primary outcome measure. VAS is the most widely used outcome measure in assessing pain due to its documented reliability and validity, ease in administration, and minimal training requirements for the administrator.

The primary effectiveness endpoint is the percentage of implanted subjects who respond to DTM SCS therapy at 3-months after device activation.

An Individual Responder is a subject that reports a decrease in upper limb pain VAS score by at least 50% at 3 months after activation of the permanent SCS system (Device Activation) as compared with Baseline measurement.

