### **B.8.3. SAFETY**

Safety will be assessed by characterizing study-related adverse events at all study visits with descriptive statistics.

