#### **B.8.3.1 DEFINITIONS**

An adverse event (AE) is any untoward medical occurrence in a subject associated with the use of the therapy under the study whether or not related to the Intellis™ SCS system or the study procedures. An AE is also any event related to any underlying medical condition, present at baseline, which increases in severity or frequency by a clinically meaningful amount during the study as determined by the Investigator. Study-related is defined as relating to device, procedure or therapy.

For all study-related adverse events, the Investigator will provide an assessment of the adverse event, its seriousness, treatment/intervention provided, relationship to the device/procedure/therapy, and resolution.

As the effectiveness measure in this study is upper limb pain, upper limb pain do *not* need to be reported as an adverse event unless it meets the definition of a serious adverse event. Investigators may, however, report any other study pain-related adverse events during the study.

A **serious adverse event** (SAE) is an adverse event that

- Leads to death
- Leads to serious deterioration in the health of the subject, that either results in
  - a life-threatening illness or injury (life-threatening is defined as at risk of death at the time of the event), or
  - a permanent impairment of a body structure or a body function, or
  - in-patient hospitalization or prolongation of existing hospitalization (in-patient hospitalization is defined as a hospital admission for a period of greater than 24 hours), or
  - medical or surgical intervention to prevent life-threatening illness or injury or permanent impairment to a body structure or a body function,
- Leads to fetal distress, fetal death, or a congenital abnormality or birth defect

An **unanticipated adverse device event** (UADE) is a serious adverse event that was not previously identified in nature, severity, or degree of incidence in the Clinical Study Plan, or any unanticipated serious problem associated with a device that related to the rights, safety, or welfare of subjects.

Known adverse events related to the device, procedure or therapy are listed in the section C. (Risk Analysis) of this Clinical Study Plan.

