***System Revision Risk:***

The Intellis Neurostimulator may require replacement in 9 years or earlier, regardless of the number of times the neurostimulator is recharged. It is possible that the system will need to be revised (explanted, replaced, or repositioned) earlier than 9 years. Possible reasons for revision/explant may include infection, malfunction, and migration of the system components. The risks associated with system revision are equivalent to the commercially available systems.

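### Explants and surgical revisions are not tabulated as an outcome, and a system removed early for lack of relief can be missed in both the responder rate and the adverse events

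*Combined protocol and SAP*

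**What the plan says.** The plan foresees loss of the device and further surgery on it. B.6.16 allows removal by the subject's choice ("At any time during the study, a subject may elect to withdraw from the study and have the SCS device system explanted") and by the investigator ("Additionally, an Investigator may elect to explant a device due to an adverse event"). Its only further instruction concerns return of the hardware. Section C.1, under System Revision Risk, adds: "It is possible that the system will need to be revised (explanted, replaced, or repositioned) earlier than 9 years". B.6.13 and B.6.14 also mention revisions and replacements, as part of routine care after the last study visit.

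The outcomes lie elsewhere. The primary endpoint in B.7.3 reads "The primary effectiveness endpoint is the percentage of implanted subjects who respond to DTM SCS therapy at 3-months after device activation", and the responder definition begins "An Individual Responder is a subject that reports a decrease in upper limb pain VAS score by at least 50% at 3 months". B.7.4 adds VAS change, disability and adverse-event frequency. B.7.5 and B.8.1 add further VAS summaries, questionnaires and device-logged activity. On safety, B.8.3 says: "Safety will be assessed by characterizing study-related adverse events at all study visits with descriptive statistics".

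Two further rules bear on the point. B.7.1 defines one analysis population: "All subjects who receive a permanent SCS system implant and complete the study without any major protocol deviations". B.8.3.1 says that upper limb pain does not "need to be reported as an adverse event unless it meets the definition of a serious adverse event", and B.8.3.2 sends only study-related events to the CRF.

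**The concern.** For a surgically implanted device, how many implanted subjects lost it or needed another operation on it is basic information about both benefit and harm. Here it matters more because the study is single-arm and open-label and its primary outcome is a self-reported pain score.

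The awkward case is the subject whose system is taken out before 3 months because it does not help. B.6.16 ties elective explant to withdrawal, so this subject does not complete the study and falls outside the B.7.1 population. The reason for removal is inadequate relief of upper limb pain, which need not be reported as an adverse event unless serious. A report that followed these rules could leave the subject out of the responder percentage and out of the adverse-event summary, with no other table showing the removal. That would be a treatment failure missing from the results meant to describe effectiveness and safety.

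**Working it through.** **1. Is explant or revision counted anywhere?** I checked each place where an outcome could be defined.

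| Place | Counts explants or revisions? |
|---|---|
| B.7.3 primary endpoint | No |
| B.7.4 secondary endpoints | No; adverse-event frequency only |
| B.7.5 additional data | No |
| B.8.1 effectiveness tests | No |
| B.8.3 safety | No; study-related adverse events only |
| B.9.2 statistical analysis | No; general descriptive statement, no rule for missing data |
| Table 1 | No row |

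**2. What happens to a subject explanted for lack of relief?**

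- *Before the 3-month visit, under B.7.1:* not a completer, so excluded.
- *Before the 3-month visit, under B.7.3:* an implanted subject, so in the denominator, but no rule classifies a subject with no 3-month VAS on the therapy.
- *After the 3-month visit:* a 3-month VAS exists. The subject is a completer if completion falls at 3 months (B.6.12, B.6.19), but not if it falls at 12 months (B.6.18).
- *Adverse events:* reporting is optional unless the pain is serious.

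**3. Size.** The plan has no explant figure to reproduce. It expects about 45 implanted (Synopsis, B.5.4.1) and about 45 completing 3 months (A.3), so its own numbers allow for 45 − 45 = 0 losses between the two.

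The rest is illustration; R and k are my assumptions. Let R be responders among 45 implanted and k be non-responders explanted before the 3-month visit. The completer rate is R/(45 − k) and the all-implanted rate is R/45. The difference is R·k / [45(45 − k)]. For example, R = 36 and k = 5 gives 180/1,800 = 10.0 points.

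| R (R/45) | k = 1 | k = 3 | k = 5 |
|---|---|---|---|
| 23 (51.1%) | 52.3% (+1.2) | 54.8% (+3.7) | 57.5% (+6.4) |
| 27 (60.0%) | 61.4% (+1.4) | 64.3% (+4.3) | 67.5% (+7.5) |
| 36 (80.0%) | 81.8% (+1.8) | 85.7% (+5.7) | 90.0% (+10.0) |

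The explant proportion itself, with exact (Clopper-Pearson) 95% limits, where the lower limit is the 0.025 quantile of Beta(x, 45 − x + 1) and the upper limit the 0.975 quantile of Beta(x + 1, 45 − x):

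- 0/45 = 0% (0 to 7.9)
- 3/45 = 6.7% (1.4 to 18.3)
- 5/45 = 11.1% (3.7 to 24.1)

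**The case against.** A reader might infer that a system removed for lack of relief must be absent from both sets of results. The documents do not support that.

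- B.7.3 is worded over implanted subjects. Read alone, it keeps the subject in the denominator. The exclusion comes from B.7.1, and the two sections conflict.
- Reporting upper limb pain is optional, not barred, and serious pain must be reported. Section C.1 lists loss of relief among the risks, and B.8.3.1 points to section C for known adverse events.
- An explant or revision done for a study-related event, such as infection or migration, is recorded as the intervention for that event (B.8.3.2).
- The Study Termination CRF records why a subject left (B.6.17), and remote contacts ask about concurrent procedures (B.6.15).

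A reader might also infer that responder rates at 6 and 12 months are inflated, or that safety rests only on retained devices. Neither follows. A responder rate is defined at 3 months only, and adverse events are captured from enrollment to study completion. Nor is explant wholly independent of perceived relief, since an unblinded subject may choose it.

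These points limit the claim to what can be missed. They do not remove it. Recording a reason or an intervention is not the same as summarising it, and no summary is specified. Optional reporting cannot give a dependable count. Even on the B.7.3 reading, the subject would at best be an unexplained non-responder and the removal would stay uncounted.

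**Conclusion.** The point holds in this form: explants and surgical revisions are not tabulated as an outcome, and an early explant for lack of relief can be missed in both the responder rate and the adverse events. The first part rests on the text alone. The second depends on reading B.7.1 as governing the primary analysis and on the investigator not reporting non-serious pain; the plan permits both and requires neither.

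The size cannot be stated from the documents. With 1 to 5 early explants among 45 and 23 to 36 responders, all assumed, the completer rate exceeds the all-implanted rate by about 1 to 10 points. The study is descriptive with no hypothesis, so no test is affected. What is affected is the main percentage and the account of what became of the devices.

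**What to change.** 1. Add to B.7.4 or B.8.3 the number of implanted subjects with (a) explant and (b) surgical revision, by reason (inadequate relief, adverse event, device problem, other) and by time from implant. At 3 months, give the proportion over all implanted with an exact 95% interval, and the number whose status is unknown. At 6 and 12 months, give the number followed to each time beside the count, or a time-to-event estimate censored at last contact. A plain percentage of all implanted would not do there: B.6.14 makes the 12-month visit optional, and Table 1 notes that some subjects consented only to 3 or 6 months. Unobserved subjects would be treated as explant-free.
2. Add an explant/revision date and reason field to the existing CRFs, covering subjects who continue after a revision. The termination form applies to those who withdraw, and the stated purposes of unscheduled visits (B.6.9) do not include surgery.
3. Reconcile B.7.1 with B.7.3, and the completion point in B.6.12, B.6.18 and B.6.19, so that the 3-month responder rate uses all implanted subjects, with those explanted before that visit counted as non-responders. Without this step the new table would leave the responder rate unchanged.

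The cost is one table, one CRF field and the text edits, with no new visit or procedure. The downside is that the reported figures may be less favourable.
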